2.2 DESCRIPTIVE STATISTICS AND VISUALIZATION

2.2.1 Descriptive statistics

For lipidomics and proteomics, the summary statistics (min, Q1, mean, median, Q3, max, SD and SEM) will be computed by group (lesional, non-lesional and healthy skin) and by visit. The summary statistics will be computed by age categories as appropriate.

For OCT, raw data and change from baseline (absolute and percent changes) will be summarized with descriptive statistics (mean, median, SD, min, max) by groups and time points. For follow-up period data, change from Week16 (or last visit prior to use of rescue treatment) will also be reported.

For FTIR, profiles over study days will be generated for individual values and group means for raw and absolute change from baseline and Week 16.

2.2.2 Data Visualization

Spaghetti plots

The biomarker profiles will be represented graphically using line plots (one line per subject). The lines will be colored by group. Additional plots will be generated by age categories as appropriate.

Profile plots

For each biomarker, the mean \pm SEM will be represented graphically by group and by visit for the absolute values and percent change from baseline. Additional plots will be generated by age categories as appropriate.

Boxplots

Longitudinal boxplots for absolute values will be provided by group and by visit. Additional plots will be generated by age categories as appropriate.

Heatmaps

A heatmap representation will be provided for each biomarker data matrix highlighting the 2 study groups (AD lesional, non-lesional and healthy volunteers) and different study visits. The age categories will be represented as appropriate. Biomarkers will be clustered according to an unsupervised clustering on Pearson correlation with Ward's agglomeration technique and a dendrogram will be added to the map. Each biomarker will be centered to the mean and reduced to the unit standard deviation. To improve the readability a separate heatmap will be generated with only the baseline biomarker levels and different groups will be highlighted.

Principal component plot

PCA plot will be conducted on log-transformed and scaled data for each biomarker data matrix. The data will be visualized on a 2-dimensional plot of first principal component (PC1) versus PC2 highlighting potential group differences and change during the study. Confidence ellipses will be added as appropriate. A scatterplot with only the baseline samples may be generated to ease the readability. Depending on the percentage of variability explained on the PC1, a second technique for deriving a composite biomarker will be applied.

Median polish

A two-way decomposition (row effect + column effect + overall effect) of the data matrix with each biomarker type will be performed using the Tukey's median polish procedure. The biomarker will be on columns and the samples on rows. The row effect will be extracted as composite biomarker.

Composite biomarker

PC1 and the row effect from the median polish algorithm will be analyzed as composite biomarkers analog to single biomarker. This includes the correlation with TEWL values, the difference between the study groups and the change during the study.

MDS and t-SNE

Multidimensional scaling (MDS) and t-distributed stochastic neighbour embedding (t-SNE) will be applied for further visualization of the data on 2 dimensions highlighting the study groups.

2.3 CLUSTER ANALYSIS

2.3.1 Patients clustering

A hierarchical clustering of AD patients will be performed on baseline biomarker data using Euclidean distance and Ward agglomeration technique. This will enable the identification of

subgroups of homogeneous patients. The identified patients' subgroups will be further investigated regarding the disease activity, disease progression and the response to the treatment (eg, longitudinal plots for mean \pm SEM of TEWL by cluster, ANOVA model for TEWL at baseline with cluster as independent predictor), cross table and Chi2-test for clusters versus categorical parameters.

For clusters definition, an elbow approach (silhouette or inertia by number of clusters) will be used for determining the optimal number of subgroups of patients using at least two different algorithms to ensure robustness (K-means and agglomerative clustering).

2.3.2 Biomarker clustering at baseline

Clustering of biomarker will be performed on biomarker expressions at baseline (using correlation-based distance metric). Biomarker clusters may be suggested to pathway analysis as appropriate. Heatmaps will be generated considering the biomarker clusters.

2.4 CORRELATION ANALYSIS

2.4.1 Correlation between biomarker and TEWL

In addition to the correlation analysis between each the composite biomarkers and the TEWL, the association between each single biomarker (lipidomics, proteomics, transcriptomics) and TEWL will be investigated at baseline in a linear model adjusted for the study group and age. TEWL at baseline will be evaluated as TEWL. Biomarker will be ranked according to their importance in explaining TEWL using RandomForest for regression. The Correlation between change in biomarker and change in TEWL, the correlation between baseline biomarker and change in TEWL will be investigated.

2.4.2 Correlation between biomarker and clinical and disease parameters

Analog to TEWL, the correlation analyses will be done between each biomarker and the relevant clinical and disease parameters. Analysis of Variance (ANOVA) will be performed for categorical variables.

2.4.3 Intra-class Correlation Coefficient

Stability of repeated measurements will be assessed for each biomarker (lipids and proteins). For each biomarker, its measurement will be modeled as:

$$Y_{ij} = \mu + \alpha_i + \beta_j + \epsilon_{ij}$$

for subject i and visit j of the subject i in a single arm (e.g., control arm) (1). Here we assume fixed visit effect β_j but random subject effect α_i and random error ϵ_{ij} . If we assume $\alpha_i \sim N(0, \sigma^2_{\text{subject}})$ and $\epsilon_{ij} \sim N(0, \sigma^2_{\text{error}})$ and independence between them, the correlation of

measurements within a subject (also known as intra-class correlation coefficient or ICC) can be derived as

$$ICC = \frac{\sigma_{\text{subject}}^2}{\sigma_{\text{total}}^2}$$

where $\sigma^2_{\text{total}} = \sigma^2_{\text{subject}} + \sigma^2_{\text{error}}$. Large ICC value indicates strong stability of repeated measurements of the biomarker of a subject.

2.5 IDENTIFICATION OF BIOMARKERS

2.5.1 Differentially expressed biomarkers

The biomarker potentially linked to the disease status (lesional, non-lesion or healthy skin) and the biomarker changing with the treatment will be identified using a linear mixed model. For each biomarker, the following model will be used to test for any interaction between group and visit for group i, visit j and subject k:

$$y_{ijk} = \mu + \text{group}_i + \text{Visit}_j + \text{group}_i \text{Visit}_{ij} + \text{Subj}_k + \varepsilon_{ijk}$$

with group, visit and interaction between group and visit considered as fixed effects and subject as random effect. Baseline will be used as reference visit and healthy skin as reference group. The data will be log-transformed. A contrast matrix will be defined for extracted the comparison of interest such as group difference at baseline or at Week 16. The fold-changes will be derived, and volcano-plots will be provided as appropriate. The intersection between biomarker differentially expressed at baseline between lesional vs. non-lesional, lesional vs healthy skin and non-lesional vs. healthy skin will be represented graphically using Venn diagrams. The proportion of biomarker changing significantly from baseline to Week 16 will be derived for each study group. The direction of the changes will be highlighted.

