1.2 STUDY DESIGN

[figure not shown]
LPS16764 is a Phase 4 open-label, exploratory study in two sites evaluating the effect of dupilumab on skin barrier function in pediatric patients aged between ≥ 6 and < 12 years old with moderate-to-severe AD. A healthy volunteer cohort will be enrolled as a reference comparator matched to AD for age-, gender-, study-site and sampling will be matched on targeted lesion area. Approximately 24 pediatric patients with moderate-to-severe AD will be enrolled to achieve 20 evaluable patients. These enrolled AD patients will receive Investigational medicinal product (IMP) dupilumab treatment during the study. Approximately 24 healthy volunteers will be enrolled to achieve 20 evaluable subjects. These enrolled healthy volunteers will not receive any IMP treatment during the study.

The maximum study duration per participant will be 32 weeks. The study will comprise of:

- Screening period 1 (Day -28 to Day -1): Participants will be evaluated according to
- Inclusion and exclusion criteria.
- Baseline visit (Week 0, Day 1): Participants who remain eligible will be enrolled.
- A 16-week treatment phase for AD patients and a 16-week observation period for healthy volunteers.
- A 12-week follow-up period.

Biomarker assessment based on lipidomics, proteomics, and transcriptomics in STS samples will be conducted at baseline (Week 0, Day 1), Week 2, Week 4, Week 8, Week 12, EoT at Week 16, and Follow-ups at Week 22 and Week 28.

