1.7 BIOMARKER ASSESSMENTS AND SCHEDULE

1.7.1 Lipidomics, proteomics, and transcriptomics

Samples for skin lipidomic assessment are required and will be collected from all participants in this study.

Targeted skin lipidomics will be performed by means of a validated mass spectrometry method from skin tapes that have been collected during tape stripping at the TEWL assessment. The detailed assessment plan for lipidomics is listed in [Section 4.1.1](#).

Protein extracts will be prepared from STS samples by LC-MS/MS. The detailed assessment plan for proteomics is listed in [Section 4.1.2](#).

Skin tapes will be collected for transcriptomic analysis. The detailed assessment plan for transcriptomics is listed in [Section 4.1.3](#).

For both AD pediatric patients and healthy volunteers, samples are collected at Week 0, 2, 4, 8, 12, 16, and 22. All STS will be conducted on the predefined spots. TEWL will be assessed before STS and after 5, 10, 15, and 20 STS in lesional and non-lesional skin (AD patients) and normal skin (healthy volunteer). Weeks and spot on which STS is conducted are

- At Weeks 0, 8, 16, and 28, STS conducted on the first spot.
- At Week 2, STS conducted on the second spot.
- At Weeks 4, 12, 22, STS conducted on the third spot.

All skin tape strips should be collected and stored.

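### The biomarker mixed model has only a random subject intercept although each AD patient gives two skin areas at repeated visits, so its standard errors for lesional versus non-lesional and for change from baseline can be wrong

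*SAP*

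**What the plan says.** Biomarker SAP 2.5.1 gives one linear mixed model per biomarker, on the log scale, "with group, visit and interaction between group and visit considered as fixed effects and subject as random effect". Group has three levels: lesional, non-lesional and healthy. The written formula has a single subject term and an error term. It has no term for skin area within a child, and no covariance structure over visits is stated.

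Biomarker SAP 1.7.1 sets out the sampling. TEWL around the stripping is assessed "in lesional and non-lesional skin (AD patients) and normal skin (healthy volunteer"), so an AD patient supplies two areas and a volunteer one. Biomarker SAP 1.2 schedules sampling at baseline and then at "Week 2, Week 4, Week 8, Week 12, EoT at Week 16, and Follow-ups at Week 22 and Week 28", which makes eight visits. Section 1.7.1 lists seven ("samples are collected at Week 0, 2, 4, 8, 12, 16, and 22"), yet its next lines assign a spot to Week 28: "At Weeks 0, 8, 16, and 28, STS conducted on the first spot".

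The uses of the model are stated in 2.5.1. "A contrast matrix will be defined for extracted the comparison of interest such as group difference at baseline or at Week 16". Biomarkers that differ at baseline between each pair of groups go into Venn diagrams, and "The proportion of biomarker changing significantly from baseline to Week 16 will be derived for each study group". Section 2.6 calls all analyses exploratory, with no formal testing.

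**The concern.** A lone subject intercept gives every pair of samples from one child the same correlation. A child's lesional samples at Week 0 and Week 16 are then treated as no more alike than a lesional sample at Week 0 and a non-lesional sample at Week 16. Any lasting deviation of one area from what is expected for that child goes into the residual, as if drawn afresh at each visit.

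A lasting deviation is plausible here, because Weeks 0 and 16 use the same spot. If it exists, comparing the two areas at one visit carries more variance than the model allows. A change within one area carries less, because the deviation cancels. The first comparison would then be called significant too often and the second too rarely, which would shift the Venn diagram and the Week 16 proportion in opposite ways.

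The clinical SAP, with the same skin-by-visit layout, at least compares several covariance structures (section 4.3.3.1). The biomarker SAP has nothing comparable.

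**Working it through.** **The plan's own figure.** No standard error or variance component is stated for this model. The only design figure is the sample size: "Approximately 24 pediatric patients with moderate-to-severe AD will be enrolled to achieve 20 evaluable patients". With the 15% drop-out in clinical SAP 1.3, 20 / 0.85 = 23.5, rounded up to 24. It reproduces.

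**Inputs.** From the documents: 20 evaluable AD patients with 2 areas, about 20 volunteers with 1 area, 8 visits. Assumed: error variance 1, subject-by-area variance A from 0.25 to 2, and at first nothing else within a child. The variance between children cancels from the contrasts tabulated below.

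**What the model estimates as residual.** A patient has 16 samples and so 15 within-child degrees of freedom. A volunteer has 8 samples and 7. That is 22 per patient–volunteer pair. One of them, the patient's mean lesional minus mean non-lesional difference, has variance 1 + 8A; the other 21 have variance 1. The fitted residual is therefore about

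e = (22 + 8A) / 22 = 1 + (8/22)A.

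**Ratio of model SE to true SE.**

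- Lesional minus non-lesional at one visit: model variance per child 2e, true variance 2(1 + A), ratio √[e / (1 + A)].
- Lesional change, Week 0 to Week 16: model variance 2e, true variance 2, ratio √e.

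The real two-sided error at a nominal 5% is 2Φ(−1.96 × ratio).

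| A | e | One-visit ratio | Real error | Change ratio | Real error |
|---|---|---|---|---|---|
| 0.25 | 1.091 | 0.93 | 6.7% | 1.05 | 4.1% |
| 0.5 | 1.182 | 0.89 | 8.2% | 1.09 | 3.3% |
| 1 | 1.364 | 0.83 | 10.6% | 1.17 | 2.2% |
| 2 | 1.727 | 0.76 | 13.7% | 1.31 | 1.0% |

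At A = 0 every ratio is 1. The visit count hardly matters: with seven visits the residual is 1 + (7/19)A, since 13 + 6 = 19, and at A = 1 the one-visit ratio is √(1.368/2) = 0.83 again. Lesional versus healthy at baseline has a ratio between 0.999 and 1.017 in the settings run.

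**Does the extra term repair it?** At A = 0.5, simulated model SEs move as follows when a subject-by-area effect is added:

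- One-visit difference: 0.345 to 0.389 (true 0.387).
- Week 16 change: 0.345 to 0.316 (true 0.316).

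**What happens with other structure.**

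- *Child-by-visit variance B*, shared by both areas at a visit. The residual becomes 1 + (8/22)A + (21/22)B, while the true one-visit variance stays 2(1 + A). The one-visit SE turns too wide once (21/22)B > (14/22)A, that is B > (2/3)A. At A = B = 0.5, e = 1.659 and the ratio is √(1.659/1.5) = 1.05.
- *Treatment response differing between children*, with variance R at Week 16 and an assumed shape over the other visits. At A = 0.5 the change ratio falls to 0.99 for R = 0.5 and 0.91 for R = 1.
- *A lasting spot effect.* With A, spot and error variances all 0.5, the change ratio is 1.47, because Weeks 0 and 16 share a spot.

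**The case against.** The strongest reply is that the plan promises no inference. Section 2.6 rules out formal testing, no significance threshold is fixed in 2.5.1, and no clinical TEWL endpoint uses this model. With complete data the estimated group-by-visit means are the same with or without the missing term; only their standard errors move. All of this stands and limits the consequence. It does not remove the point, because 2.5.1 reports which biomarkers differ and what share change significantly, and those outputs depend on the standard errors.

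A reader might infer that lesional versus non-lesional is always declared too easily and treatment change always too rarely. The documents do not support that. They give no variance components, and the checks with B and R show that each direction can reverse under plausible variation.

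A reader might also look to a lesional minus non-lesional difference averaged over all visits, where the error is severe: at A = 1 the ratio is √[(1.364/8) / (1 + 1/8)] = 0.39, so a 95% interval covers about 55%. The plan leaves other contrasts open but names none averaged over visits, so that figure should not stand for the planned analysis.

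Scope is narrower too. Biomarker SAP 2.1.1.3 sends differential testing of transcripts to DESeq on raw counts, so the point bears mainly on lipids, proteins and filaggrin breakdown products.

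**Conclusion.** The point holds in conditional form. The stated model omits a level of the design, skin area within AD patient, and nothing elsewhere in the biomarker SAP supplies it. If areas differ persistently within a child and no other within-child structure is present, the SE for lesional versus non-lesional at one visit is 7% to 24% too small, and the SE for lesional change to Week 16 is 5% to 31% too large, for A from 0.25 to 2 times the error variance. The error is modest at the single visits the plan names and close to nil for lesional versus healthy at baseline. The variance ratios are assumptions, and the signs depend on them. The reversals offer no defence of the stated model, since they come from further within-child variation that it also leaves out. The consequence is confined to an exploratory screen, but one that counts significant biomarkers.

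**What to change.** In biomarker SAP 2.5.1, add a random subject-by-skin-area effect nested in subject: group, visit and group-by-visit fixed; subject and subject-by-area random; then error. Take all contrasts in that section from this model. State the residual covariance structure, and say how it will be checked whether a subject-by-visit term or an area-specific covariance over visits is also needed, because the nested term alone does not cover shared visit variation or differing response between children. State which data types use this model and which use DESeq.

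The cost is a line or two in the plan and in the code, with no new data. The downside is one or two more variance components per biomarker. With about 20 patients some will be estimated at zero, and the model then reduces to the present one.

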2.5.2 Discriminative biomarkers

A multivariate predictive panel will be identified used Elastic-net penalized multinomial logistic regression and the predictive value of the panel will be estimated as 10-fold cross-validated as accuracy. Biomarkers will be ranked according to their importance in discriminating between Lesional, non-lesional and healthy skin groups as provided by RandomForest.

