2.5.3 Predictive biomarkers

In case of any binary response defined a clinical endpoint, the predictive characteristics for each biomarker will be evaluated using a logistic regression model with the baseline biomarker and the response variable as binary outcome at Week 16. For the binary response at Week 16, a multivariate predictive panel will be identified used Elastic-net penalized logistic regression and the predictive value will be estimated as 10-fold cross-validated Area Under the ROC curve. These analyses will be computed for AD patients (lesional skin). Biomarkers will be ranked according to their importance in discriminating between responders and non-responders as

provided by RandomForest. A linear model will be used for change from baseline in clinical responses as continue parameters and baseline biomarker level.

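### Biomarker SAP 2.5.2 and 2.5.3 rely on plain 10-fold cross-validation without requiring folds by child or stratification, so the reported accuracy and AUC can be biased with no signal.

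*SAP*

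**What the plan says.** Biomarker SAP 2.5.2 builds an elastic-net multinomial panel for "discriminating between Lesional, non-lesional and healthy skin groups". Its only performance measure is the panel's predictive value, "estimated as 10-fold cross-validated as accuracy". The section names no visit.

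Biomarker SAP 2.5.3 applies if some clinical endpoint is defined as a binary response. It uses a "logistic regression model with the baseline biomarker and the response variable as binary outcome at Week 16", fits an elastic-net panel, and states that "the predictive value will be estimated as 10-fold cross-validated Area Under the ROC curve". It is restricted to lesional skin in AD patients.

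Both sections also rank markers by random forest importance, but a ranking does not measure performance. Neither section states the fold unit, stratification, repeats, nesting of the penalty choice or an interval. Section 2.5.3 does not say whether the AUC is pooled or averaged over folds.

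On numbers, biomarker SAP 1.2 says: "Approximately 24 pediatric patients with moderate-to-severe AD will be enrolled to achieve 20 evaluable patients". It gives the same figures for healthy volunteers and lists eight tape-strip sampling times (Weeks 0, 2, 4, 8, 12, 16, 22 and 28).

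**The concern.** Cross-validation estimates performance in new children only if the held-out data are independent of the training data. In 2.5.2 they need not be. An AD child gives a lesional and a non-lesional sample, possibly at several visits, and a split by sample scatters them over training and test sets.

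- With visits pooled, the training set holds other samples of the same child and skin area with the right label, so recognising the child helps.
- At baseline only, the child's one other sample carries the other label, so recognising the child hurts.

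In 2.5.3 the difficulty is different. With two patients in a test fold, often both have the same outcome. An AUC within such a fold cannot be computed. Pooling predictions over folds keeps the AUC defined, but removing two responders makes responders rarer in that training set and pushes the held-out scores the wrong way.

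These figures are the only stated evidence on whether either panel works. A biased one could start or stop follow-on biomarker work.

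**Working it through.** **1. Numbers of children.** The clinical SAP (1.3) allows 15% drop-out: 20/(1 − 0.15) = 23.5, rounded up to 24. The plan's own figure reproduces.

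**2. Fold sizes with 10 folds.**
- 2.5.3: 20 to 24 AD patients give 2.0 to 2.4 per fold.
- 2.5.2: 40 to 48 children give 4.0 to 4.8 per fold. With 20 evaluable per cohort, baseline samples number 20 × 2 + 20 = 60, so 6 per fold. Eight visits give 480.

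**3. Separation of a child's samples in 2.5.2.** In a random split of 60 baseline samples into folds of 6, an AD child's other sample lands in a different fold with probability 54/59 = 92%.

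**4. Accuracy in 2.5.2 with no group signal.** Always naming one class scores 20/60 = 0.33. The simulation used a three-class elastic net, 20 AD and 20 healthy children, 100 markers, a fixed penalty and total variance 1. There were 150 data sets for baseline only and 25 for eight visits. The marker count and correlations are assumptions; the documents give none.

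| Samples used | Child correlation | Skin-area correlation | Folds by sample | Folds by child |
|---|---|---|---|---|
| 8 visits pooled | 0.5 | 0 | 0.50 | 0.32 |
| 8 visits pooled | 0.3 | 0.3 | 0.68 | 0.32 |
| Baseline only | 0.5 | 0 | 0.24 | 0.33 |
| Baseline only | 0.3 | 0.3 | 0.26 | 0.31 |

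A further set of runs gave 0.48 to 0.78 pooled and 0.23 to 0.27 at baseline by sample, against about 0.32 to 0.33 by child. Rounded, the ranges are 0.5 to 0.8 and 0.23 to 0.27.

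A plausibility check: with visits pooled, a rule that recognised every child perfectly but not the skin area would get all 160 healthy samples and half of the 320 AD samples right, (160 + 160)/480 = 0.67, with no group signal. Recognising the skin area as well takes it higher.

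**5. One-class folds in 2.5.3.** For k responders among 20 and a random fold of two, the share is [k(k − 1) + (20 − k)(19 − k)]/(20 × 19).
- k = 10: (90 + 90)/380 = 47%.
- k = 14 (or 6): (182 + 30)/380 = 56%.

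In 20,000 random splits, at least one such fold occurred in over 99%. With 24 patients the share was 37% to 48% (12, 16 or 7 responders).

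**6. AUC in 2.5.3 with no signal.** Simulated with 20 patients, 10 responders, 100 independent markers and 200 data sets:

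| Method | Mean AUC | 95% range |
|---|---|---|
| 10-fold, pooled predictions | 0.42 | 0.09 to 0.85 |
| 10-fold, averaged over usable folds (about 5 of 10) | 0.49 | 0 to 1 |
| Stratified 5-fold, 3 repeats | 0.50 | 0.18 to 0.80 |

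A separate check gave about 0.40 for pooled 10-fold and about 0.47 to 0.50 for repeated stratified 5-fold.

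**7. Limit set by 20 patients.** Even for a fixed score, the null AUC has SD √[(n + 1)/(12·n₁·n₀)]. With 10 and 10 this is √(21/1200) = 0.13; with 14 and 6 it is √(21/1008) = 0.14.

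**The case against.** Several stronger readings are tempting, and the document does not support them.

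- **That the plan forms folds by sample.** It does not say so. Biomarker SAP 2.4.3 (intra-class correlation) and 2.5.1 (random subject effect) show that its authors know the samples are correlated. The fault is that 2.5.2 does not require folds by child.
- **That the accuracy will be inflated.** This needs pooled visits, which 2.5.2 does not state. Clustering (2.3) and the single-marker TEWL model (2.4.1) use baseline data, and pooling would put untreated and treated lesional skin in one class. With baseline only, the bias runs downward.
- **That leakage also affects the AUC.** In 2.5.3 each child has one baseline lesional record, so folds by sample and folds by child coincide. Conversely, two patients per fold is a feature of 2.5.3 and not of 2.5.2.
- **That the AUC cannot be computed at all.** This holds fold by fold. A pooled AUC fits the text and is always defined, although biased.

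Three further points stand. Section 2.5.3 may never be run, because section 1.3.3 lists no binary response. Section 2.6 calls every analysis exploratory, and no TEWL endpoint depends on these panels. The sizes in 2.5.2 rest on assumed correlations.

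Exploratory status removes any concern about formal testing. It does not make a biased performance figure readable.

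**Conclusion.** The point holds as a gap that should be closed. Ordinary splitting by sample, which 2.5.2 allows, biases the null accuracy under either reading of the visits. It rises to about 0.5 to 0.8 with eight visits pooled and falls to about 0.23 to 0.27 at baseline, against about 0.32 with folds by child. This assumes child correlations of 0.3 to 0.5, skin-area correlations of 0 to 0.3 and 100 markers. As neither the visits nor the fold unit is fixed, a reader could not tell the direction of the error.

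In 2.5.3, if it is run, unstratified 10-fold is a poor choice however the AUC is combined. With 6 to 14 responders among 20 patients, 47% to 56% of folds give no AUC, and pooling centres the null at about 0.40 instead of 0.50.

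The consequence is limited to exploratory biomarker conclusions.

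**What to change.** In biomarker SAP 2.5.2, assign folds by participant, keeping all samples of a child together and balancing folds by cohort. Name the visit or visits used.

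In 2.5.3, replace 10-fold with repeated stratified 5-fold cross-validation. Compute the AUC on pooled out-of-fold predictions and report an interval.

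In both, choose the penalty and do data-driven preprocessing inside the training folds. This matters for section 2.1.2.1, where a marker with 25% to 50% of values below the quantification limit is kept only if a Fisher test links them to the group. That step uses the class labels; its effect was not quantified here.

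The cost is a participant identifier in the fold assignment, slightly more computing and slightly smaller training sets (16 of 20 patients instead of 18 in 2.5.3). No new data are needed. The change removes most or all of the bias but not the imprecision: with about 20 patients, a null AUC still ranges from about 0.2 to 0.8, and the report should say so.
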